This marks the end of the 6-week study period. Clinical data (HbA1c) along with total daily insulin requirement and pump settings at the end of the study will be collected. Short questionnaire asking for feedback using the 780G pump with SmartGuard, will be given to parents (optional).

[figure not shown]
Wash-out period: There should be a minimum wash-out period of 3 months for participants willing to enrol for the larger RCT. The 3-month period is chosen to minimise the impact of any carry over of glycaemic impact with AHCL into the larger RCT.

Randomized Controlled Trial (RCT) Phase

This is a **prospective multicentre randomised controlled, two-arm unblinded, parallel study** in free-living conditions, in young children with type 1 diabetes on insulin pump therapy. Participants will be randomised in two groups; either the control group (standard therapy) or the intervention group (AHCL). The control group will be participants on continuous subcutaneous insulin infusion (CSII) with or without CGM (continuous glucose monitoring). The study duration is for 3 months. This phase will be conducted at four tertiary paediatric diabetes centres (Perth Children’s Hospital, WA, Westmead Children’s Hospital, NSW, Women’s and Children’s Hospital, SA, and Royal Children’s Hospital, VIC).

AHCL group: Investigational pump for 3 months OR Control group: Standard CSII for 3 months.

The study design is as shown in the Figure 2 as below.

*Visits 2B,2C, 5C, 5D optional if data requirement from blinded CGM not met, Visit 5 Blinded CGM only for control group.

Figure 2: Study design RCT

VISIT 1

(Eligibility Confirmation, Baseline data collection and commencement of run-in period).

Information sheets will be provided in advance to participants who potentially fit inclusion criteria. HbA1c should be available from last clinic visit within 3 months of Visit 1.

Participants will be checked if they meet the inclusion criteria listed below in Section 5.2. The following data will be recorded:

1. Consent signed by parent and investigator
2. Auxology
 - a. Height
 - b. Weight
 - c. BMI
3. Demographic
 - a. Date of Birth
 - b. Gender
4. Diabetes clinical
 - a. Date of diagnosis
 - b. Current pump/CGM therapy
 - c. HbA1c
 - d. History of severe hypoglycaemia – coma or convulsion or episodes requiring third party assistance (events in last 12 months).
 - e. History of diabetic ketoacidosis (DKA) in the last 12 months

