 - a. HbA1c
 - b. Total daily dose of insulin (mean of previous 7 days)
 - c. Severe hypoglycaemia in the run-in period
 - d. Diabetic ketoacidosis in the run-in period
 - e. Hospital admissions in the run-in period
2. Review carbohydrate (CHO) counting and offer dietetic support if needed
3. Pump upload and review of settings
4. Review of hypoglycaemia/hyperglycaemia management.

The control group will continue on their insulin pump therapy with or without CGM. They will attend the 3-monthly regular clinic appointments.

The intervention group will use the study device with the compatible CGM. They will attend additional visits required for device training and to review the pump settings. They will continue to attend their 3-monthly clinic appointments.

If needed, Visit 3 and 4A can be combined for intervention group.

VISIT 4 (Only for participants randomised to AHCL arm)

The additional visits for the HCL group are for device training to support the use of HCL.

Visit 4A: Pump training (2 hours)

Parents will be trained on how to use the Medtronic 780G insulin pump. They will be provided with a compatible meter (which communicates with the pump) along with the glucose strips for the study.

Visit 4B: CGM training (2 hours)

They will be instructed on how to link CGM on the Medtronic 780G pump and issued with compatible next generation sensor and transmitter, as well as CGM user guide. Initial low and high alarms will be set at 4.0mmol/L and 15mmol/L respectively, although these can be changed according to individual preference. Sensor naïve individuals will have familiarisation phase of 7 to 10 days to get used to wearing a sensor.

Visit 4A and 4B could be combined for participants familiar with sensors.

Visit 4C: Commencement of AHCL (1-2 hours)

Once CGM data has been established for a minimum of 3 to 7 days, participant returns for face-to-face instruction on AHCL use and initiation of 'SmartGuard'. During this visit, the sensor will be replaced to demonstrate sensor warm up and AHCL initiation, and provide an opportunity for those unfamiliar with CGM use to practice a sensor change with supervision.

Participants will subsequently have weekly communication via phone call or email for support for the following 4 weeks, and upload their pump weekly. Investigators will log all time spent training and in communication with participant. Communication can be more often – as per clinical need, and logged.

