Visit 4D: Review of AHCL (after 4 weeks from commencement of AHCL, 1 hour)

Face-to-face meeting to upload insulin pump, review CareLink reports and revise settings (CHO ratio and Insulin action time)

Participants will be issued with enough consumables for the study.

Research staff will review CGM data at 8 weeks' with participants encouraged to contact the team if support/assistance required.

VISIT 5 (11 weeks after randomisation for control arm only)

Visit 5A: Insertion of blinded CGM: This constitutes first of the two sensors, each sensor provides data for 7 days. Parents will be instructed to test their children for a minimum 3 to 4x/day using the study meter.

Visit 5B: Insertion of 2nd blinded CGM: Participants will return 7 days after sensor insertion to remove and download the first week of CGM data. The study meter will be uploaded. A new sensor will be inserted and a fresh transmitter attached.

A total of 2 weeks of blinded sensor is required with at least 10 days of data. In participants who do not meet this requirement, repeat sensors will be offered till a maximum of 4 attempts of data collection

Visit 5C: Insertion of 3rd blinded sensor (if applicable)

Visit 5D Insertion of 4th blinded sensor (if applicable)

VISIT 6 (1 week after last blinded sensor) **End of RCT Phase**

The following data will be collected:

1. Auxological
 - a. Height
 - b. Weight
 - c. BMI
2. Diabetes clinical
 - a. HbA1c
 - b. Total daily dose of insulin (mean of previous 7 days)
 - c. Pump upload (for intervention group)
 - d. Severe hypoglycaemia since Visit 5 for Control arm / Visit 4d for Intervention arm
 - e. Diabetic ketoacidosis since Visit 5 for Control arm / Visit 4d for Intervention arm
 - f. Hospital admissions since Visit 5 for Control arm / Visit 4d for Intervention arm
3. Psychology measures: Psychological scales will be administered to parents on an electronic platform.
 - a. Functional health status: Quality of life (QOL) WHO 5, EQ5D
 - b. Fear of hypoglycaemia: Hypoglycaemia fear survey Parent
 - c. Diabetes-related distress: Problem Areas in Diabetes PAID-Parent version
 - d. Anxiety: GAD-7
 - e. Sleep quality: Pittsburgh Sleep Quality Index
 - f. Technology acceptance and satisfaction: DTQ
4. 24-hour food recall interview (to capture dietary pattern)
5. Parents of participants will be offered a semi-structured interview at the end of the study to share the lived experiences with use of new technology.

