6.3 Monitoring of participant compliance

The study is targeted at young children primarily supervised by parents/caregivers and hence a high degree of engagement with the study is expected.

Participants using the AHCL device will receive support from the research staff to help them familiarise themselves with the AHCL system. As this cohort is already on insulin pump therapy with most of the children on sensors, adaptation of this technology is not expected to be challenging.

Parents will also receive assistance to help troubleshoot sensor issues. They will be able to upload the pump at home, review reports and this will provide an opportunity to engage and encourage the use of the system.

7 Assessment of Efficacy

The efficacy of the device will be assessed through the Randomised Controlled Trial. 7.1 Primary outcomes

The primary outcome is the percentage of time spent in target glucose range (3.9-10 mmol/L) measured at 5-minutely intervals by a blinded CGM over 2 weeks starting at 13 - 15 weeks post randomization. Percentage of time spent in target glucose range will be calculated by dividing the number of sensor readings falling in the range 3.9-10 mmol/L by the total number of sensor readings and multiplying by 100. Participants will be considered to have missing data if they have fewer than 10 days with 70% valid sensor readings.

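### Repeat sensors are offered to controls only, but one data-sufficiency rule sets the primary outcome to missing in both arms, so missingness can differ by arm and may depend on device use in AHCL

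*Protocol*

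**What the plan says.** **Follow-up collection, control arm (4.2, RCT Phase).** The visit is headed "VISIT 5 (11 weeks after randomisation for control arm only", and the note under Figure 2 repeats this: "Visit 5 Blinded CGM only for control group". Two sensors are planned, and "each sensor provides data for 7 days". If 10 days of data are not reached: "In participants who do not meet this requirement, repeat sensors will be offered till a maximum of 4 attempts of data collection". Visits 5C and 5D are the third and fourth sensors.

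**Follow-up collection, AHCL arm (4.2).** "The intervention group will use the study device with the compatible CGM". At Visit 4D, "Participants will be issued with enough consumables for the study". The pump is uploaded at Visit 6. No repeat or extension rule is given.

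**Primary outcome, both arms (7.1).** Time in range is "measured at 5-minutely intervals by a blinded CGM over 2 weeks starting at 13 - 15 weeks post randomization". No arm is named. Then: "Participants will be considered to have missing data if they have fewer than 10 days with 70% valid sensor readings".

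**Missing data (9.1, 9.7).** Multiple imputation under a multivariate normal model, with complete-case results also presented.

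**Baseline, for comparison (4.2, Visit 2A).** Before randomisation the four-attempt allowance applies to every child.

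**The concern.** The threshold for having a primary outcome is common to both arms, but the written chance of reaching it is not. The baseline procedure shows that the planners expected two sensors sometimes to fall short. Children who needed a third or fourth sensor to qualify are randomised to both arms, yet only those in the control arm keep the allowance at follow-up.

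In AHCL the sensor that supplies the outcome also drives the algorithm, so a day without sensor data is a day without closed loop. Section 4.9 keeps children who stop AHCL in the study, and section 8.2(f) sends those with pump failure back to their own pump. Neither group is scheduled for follow-up blinded sensors. If such children drop out of the observed data, the AHCL outcomes that remain come disproportionately from better users, in a trial whose primary analysis is by intention to treat. Missing-at-random imputation corrects this only as far as the imputation model captures device use.

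**Working it through.** **1. The plan's own figures.** The protocol states no expected wear or missingness. The only loss figure is the 10% dropout in 9.2: 2 × 31 = 62, and 62 / 0.9 = 68.9, consistent with the planned 70. The sample size does not depend on this point.

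**2. Sensor-days available.**
- Control: 2 × 7 = 14 days, up to 4 × 7 = 28.
- AHCL: 14 days if the two weeks of 7.1 are taken as fixed. This is an assumption, because the text does not fix them.

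**3. Equal daily validity, no replacement within the window.** Let p be the chance that a day is valid (assumed). With independent days, P(missing) = P(X ≤ 9) for X ~ Binomial(d, p). For p = 0.85 and d = 14, the probabilities of 10, 11, 12, 13 and 14 valid days are 0.0998, 0.2056, 0.2912, 0.2539 and 0.1028. They sum to 0.9533, so P(missing) = 4.7%. Where days correlate within a child (assumed correlation 0.1 to 0.2), a beta-binomial is used instead.

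| p | 14 days, independent | 14 days, corr. 0.1–0.2 | 28 days, independent | 28 days, corr. 0.1–0.2 |
|---|---|---|---|---|
| 0.75 | 25.9% | 31–32% | 0.0% | 1.3–4.9% |
| 0.80 | 13.0% | 21–24% | 0.0% | 0.5–2.9% |
| 0.85 | 4.7% | 13–16% | 0.0% | 0.2–1.6% |
| 0.90 | 0.9% | 6–10% | 0.0% | 0.1–0.7% |
| 0.95 | 0.04% | 2–4% | 0.0% | 0.0–0.2% |

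The 28-day columns assume that every family accepts all the sensors offered.

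**4. Unequal validity.** With independent days, 14 days at p = 0.85 gives about the same missingness as 28 days at p = 0.50 (about 4.4%). The arms balance if AHCL children wear sensors much more reliably.

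**5. Replacement within the window.** A second model, by simulation: a sensor lasts 7 days or, with probability f, fails after 0 to 6 days. Controls get four scheduled sensors. AHCL families replace a failed sensor after a gap, inside a fixed 14 days. Both f and the gap are assumptions.

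| f | Control, 4 sensors | AHCL, 1-day gap | AHCL, 2-day gap | AHCL, 4-day gap |
|---|---|---|---|---|
| 0.1 | 0.0% | 0.0% | 0.1% | 1.1% |
| 0.3 | 0.4% | 0.0% | 1.6% | 9.4% |
| 0.5 | 2.4% | 0.3% | 7.6% | 25.2% |

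With next-day replacement AHCL is no worse than control, and the order can reverse. With gaps of 2 to 4 days AHCL is worse.

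**6. Illustration in time-in-range points.** Suppose the missing AHCL children average 8 points below those observed, that is, they lose the whole effect assumed in 9.2. A complete-case AHCL mean is then too high by (fraction missing) × 8: 0.047 × 8 = 0.4 points to 0.163 × 8 = 1.3 points. The 8-point gap is assumed, not documented.

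**The case against.** A reader might infer that AHCL children have only a single fixed two-week window, that missingness is therefore higher in AHCL by construction, and that the result is biased in its favour. The documents do not support that much.

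- Section 7.1 names no arm and lets the window start anywhere from week 13 to week 15. AHCL sensor data accrue throughout, and no passage forbids a later start.
- The repeat rule fits how controls are measured: sensors placed and removed at clinic visits a week apart. AHCL families practise sensor changes, hold supplies and receive troubleshooting help, so they can replace a sensor within the window.
- Repeats are only offered to controls, and some families will decline.
- The 13–16% figure at p = 0.85 needs an assumed correlation. With independent days it is 4.7%.
- Missing outcomes are imputed, and complete-case results are shown beside them. A child with too little sensor data is also not the same as a dropout under 9.2.

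All of this stands against the claim of a fixed direction or size. It does not remove the asymmetry. Prompt replacement is not required anywhere. A movable start with no selection rule, in an unblinded trial, leaves the AHCL window open to choice. An analysis plan could define the AHCL window, but it cannot recover sensor data never collected from children who have left the device.

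**Conclusion.** The point holds in a limited form. The protocol writes a repeat allowance for one arm and a single missing-outcome rule for both, with no matching provision for AHCL. Primary-outcome missingness can therefore differ by arm and, in AHCL, may depend on device use.

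Direction and size cannot be determined from the protocol. At 85% valid days in both arms and no replacement, the contrast is about 5–16% against 0–1.6%. It is negligible at 95% validity with independent days, and absent or reversed with next-day replacement. That low users would be the ones lost, and that this would flatter AHCL, is a reasonable inference from the device's design and not something the protocol states. The defect should be corrected because the remedy is small. It does not by itself undermine the trial.

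**What to change.** In 7.1, set one assessment window and one sufficiency rule for both arms:

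1. Start the AHCL data at the same post-randomisation week as the control sensors. This needs week 11 in Visit 5 reconciled with the week 13 to 15 start in 7.1. Two control sensors begun at week 11 end at week 13, just as the 7.1 window opens.
2. Correct the reference in 7.1 to blinded CGM, since AHCL has none at follow-up.
3. If a child in either arm has fewer than 10 valid days in the first 14, add the following weeks one at a time, to at most 28 days. For AHCL, use the study CGM data in the Visit 6 pump upload.
4. Report days used and missingness by arm.

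The extension must stay within the period before Visit 6 and device return. Counted from weeks 13 to 15, 28 days would run to weeks 17 to 19, beyond the three-month device period. Counted from week 11 it would run to week 15.

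**Cost.** Slightly more data processing. Visit 6 is timed from the last blinded sensor, which AHCL children do not have, so its AHCL timing must be aligned with the control schedule. Children no longer using the study CGM would still lack data unless they are also offered the control-style sensors, at the cost of some added visits and sensors.

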8.2 Safety

This is a cohort of young children with T1D supervised by their parents/caregivers.

Participants will be contacted on a weekly basis (or more frequently as required) during the entire duration of the feasibility phase and for at least 4 weeks of the larger RCT after commencement of AHCL to review progress. During the feasibility phase, the research nurse will also follow the participant in real-time. Real-time glucose levels will also be available to the caregiver/parent at all times.

- a. Participants with high blood/sensor glucose levels will be advised to test for blood ketones.
- b. Participants with hypoglycaemia will be advised to take appropriate clinical action.
- c. Weekly review of time spent in hypoglycaemia range will be evaluated by the research doctor. Any instance of a week where percentage of time spent <3.9 mmol/l exceeds 8% and/or percentage of time <3 mmol/L exceeds 2 % will be recorded as an adverse event.
- d. Participants using the AHCL system will be informed to contact the research diabetes educator if they experience technical issues with the sensor and/or system and to revert to manual mode (standard pump) in the interim.
- e. Participants in the control group will be advised to follow the clinical pathway while participants in the intervention group will be advised to contact the research doctor/diabetes educator.
- f. In the event of device (pump) failure, the participant will be advised to switch to their standard pump therapy (own pump) and contact the research doctor/diabetes educator.
- g. Patients are educated regarding awareness of insulin infusion failure (rising blood glucose levels and ketones) and how to manage this (using standard injected subcutaneous insulin, and change insulin infusion set).
- h. Any admissions to hospital for DKA or severe hypoglycaemia will be reported to the principal investigator within 24hrs with notification to the lead site.
- i. Establishment of Data and Safety Monitoring Board (DSMB) to review progress

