Continuous secondary outcomes (glycaemic, auxological, clinical, psychosocial) will be analysed using the ANCOVA approach described above. The same assessment of model residuals will be conducted, and the appropriate analysis approach utilised. Where parametric methods are employed using the untransformed outcome measure, mean difference with 95% CI will be presented; where data are transformed, the retransformed effect with 95% confidence intervals will be presented as an indication of the relative effect of the intervention; where non-parametric methods are employed, Hodges-Lehmann median difference with robust 95% CI will be presented.

Secondary count outcomes will be analysed using Poisson regression or, where overdispersion is apparent, negative binomial model with a maximum likelihood-estimated dispersion parameter. 'Exposure' will be the number of hours wearing the sensor for CGM-derived outcomes and total number of days enrolled in the study for non-CGM-derived outcomes.

To assess the cost effectiveness of the intervention, the 'cost per quality of life year (QALY)' will be calculated using an incremental cost effectiveness ratio.

All hypothesis testing will be two-sided with an α of 0.05. No corrections for multiplicity are planned to control Type I error; rather, the effectiveness of the intervention will be assessed based on the clearly specified primary outcome; secondary outcomes are exploratory in nature and will be labelled as such in publications arising from the study.

No interim analyses are planned apart from the DSMB safety review reported above.

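### Visit 6 asks about severe hypoglycaemia, DKA and admissions over different periods in the two arms, neither starting at randomisation, while exposure for non-CGM counts is total days enrolled

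*Protocol*

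**What the plan says.** Protocol section 4.2, RCT Visit 6, items 2d to 2f, sets a look-back that depends on the arm for three kinds of event:

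- "Severe hypoglycaemia since Visit 5 for Control arm / Visit 4d for Intervention arm"
- "Diabetic ketoacidosis since Visit 5 for Control arm / Visit 4d for Intervention arm"
- "Hospital admissions since Visit 5 for Control arm / Visit 4d for Intervention arm"

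The two anchor visits are far apart in time. The control anchor is headed "VISIT 5 (11 weeks after randomisation for control arm only"). The AHCL anchor is "Visit 4D: Review of AHCL (after 4 weeks from commencement of AHCL, 1 hour"), and AHCL itself starts at Visit 4C, "Once CGM data has been established for a minimum of 3 to 7 days".

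Visit 3 collects the same three events, but for the run-in only. The lists for Visits 4A to 4D and 5A to 5D contain no such item. The feasibility phase states that adverse events are logged at each visit; the RCT visit descriptions have no equivalent sentence.

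Section 9.1 models secondary counts by Poisson or negative binomial regression, with exposure equal to "total number of days enrolled in the study for non-CGM-derived outcomes".

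Outside the visits, section 8.2(h) says: "Any admissions to hospital for DKA or severe hypoglycaemia will be reported to the principal investigator within 24hrs". Section 4.9 has the DSMB told of hypoglycaemia events in real time, and section 8.4 lists severe hypoglycaemia, severe DKA and inpatient stays as severe adverse events.

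**The concern.** A rate is interpretable only if numerator and denominator cover the same time. Here the listed question covers the last few weeks in controls and more than half of follow-up in AHCL under the planned schedule, while the stated denominator is the whole enrolment in both arms. A between-arm ratio built that way partly measures how long each family was asked about.

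The gap also matters within the AHCL arm. The period from randomisation to Visit 4D includes pump training, the switch to automated delivery and the first four weeks of use, when device problems might be expected to show. No listed visit asks about these events in that period.

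At stake are the descriptive safety comparison for a device the protocol calls investigational, in children aged 2 to 7, and the hypoglycaemic-event and admission items among the health-economic outcomes in section 4.1. An analysis plan can redefine the exposure, but it cannot supply events nobody asked about.

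**Working it through.** The protocol gives no event rate or window length, so there is no stated figure to reproduce. The check rebuilds the timeline in weeks from randomisation.

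**Inputs**

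- Control window opens at week 11 (section 4.2, Visit 5).
- AHCL window opens four weeks after Visit 4C. Visit 4A may coincide with Visit 3, and Visit 4C needs at least 3 to 7 days of CGM data, so Visit 4C can be at day 3 (week 0.43) or week 1. For sensor-naive children, 7 to 10 days of familiarisation plus 3 to 7 days of CGM data gives up to 17 days (week 2.4). Week 3 is taken as a late bound, which is an assumption. Visit 4D is then at week 4.43 to 7.
- Control Visit 6 is one week after the last blinded sensor. With two sensors (inserted at weeks 11 and 12) that is week 13 if counted from insertion and week 14 if counted from removal. With four sensors it is week 15 or 16.
- AHCL Visit 6 is not defined, because only controls have Visit 5 sensors. Week 13 to 14 is assumed from the three-month duration. Repeat control sensors do not delay AHCL participants.

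**Formula.** With equal constant true rates and Visit 6 as the only source,

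expected ratio (AHCL/control) = (AHCL window ÷ AHCL days enrolled) ÷ (control window ÷ control days enrolled).

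| Visit 4D (week) | Visit 6 control (week) | Visit 6 AHCL (week) | Control window, weeks (share) | AHCL window, weeks (share) | Ratio |
|---|---|---|---|---|---|
| 5 | 13 | 13 | 2 (15%) | 8 (62%) | 4.0 |
| 5 | 14 | 14 | 3 (21%) | 9 (64%) | 3.0 |
| 7 | 13 | 13 | 2 (15%) | 6 (46%) | 3.0 |
| 7 | 14 | 14 | 3 (21%) | 7 (50%) | 2.3 |
| 5 | 16 | 14 | 5 (31%) | 9 (64%) | 2.06 |
| 7 | 16 | 13 | 5 (31%) | 6 (46%) | 1.48 |
| 4.43 | 13 | 14 | 2 (15%) | 9.57 (68%) | 4.44 |

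The base case is (8/13) ÷ (2/13) = 4.0. The extremes are (6/13) ÷ (5/16) = 1.48 and (9.57/14) ÷ (2/13) = 4.44.

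**Run-in.** If days enrolled also counted a two-week run-in, the extremes become (6/15) ÷ (5/18) = 1.44 and (9.57/16) ÷ (2/15) = 4.49. Whether the run-in counts therefore hardly matters.

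**Absolute rates.** The share columns are also the fraction of the true rate each arm would report: in the base case 15% in controls and 62% in AHCL.

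**After correction.** If both windows open at randomisation and exposure covers the same days, each share is 1 and the ratio is 1.0.

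**The case against.** A reader might infer that the primary safety outcome itself is compared over unequal windows, that most control events would never be recorded, and that the trial is firmly biased against AHCL. The protocol does not support any of these.

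- Severe hypoglycaemia as the primary safety outcome is handled in section 4.9 by sequential monitoring with real-time DSMB notice, not by the count model. The exposure rule in section 9.1 is for secondary counts. Section 4.1 lists neither severe hypoglycaemia nor DKA by name; the nearest items are hypoglycaemic events and diabetes-related admissions under health economics. Nothing says the Visit 6 fields are the only source for those counts.
- Section 8.4 defines these events as severe adverse events in either arm, including a glucagon-treated episode at home, which the 24-hour admission rule alone would miss. Some events in the gap should therefore surface.
- The direction depends on a constant event rate. If AHCL events cluster in the first weeks on the device, the Visit 6 fields would hide them, and the distortion could favour AHCL.
- The look-back may have been meant as time since last asked, with the item accidentally left out of the Visit 4D and Visit 5 lists.

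All four points stand as limits on the conclusion. They do not remove the mismatch. The other routes depend on staff learning of the event, and that chance is unequal: AHCL families have weekly contact for four weeks and are told to call the research team, while section 8.2(e) sends controls to the usual clinical pathway. On the accidental-omission reading, the listed visits still leave the same gap.

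**Conclusion.** The point holds in a limited form. The listed RCT visits ask about severe hypoglycaemia, DKA and admissions over about 2 to 5 weeks in controls and 6 to 9.6 weeks in AHCL, leave the earlier period uncovered in both arms, and are paired with an exposure covering the whole enrolment.

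The expected null ratio of about 3 to 4 (Visit 4D at week 5, Visit 6 at week 13 to 14), and the wider 1.5 to 4.4, rest on three assumptions: Visit 6 fields as the sole source, equal constant rates, and an assumed AHCL Visit 6 date. Outside those assumptions neither size nor direction is fixed. What can be said is that, from the listed visits, absolute rates are understated in both arms and the between-arm comparison cannot be relied on.

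This should be fixed, but it is not critical to the main result. The CGM primary outcome is untouched, and section 9.1 declares the secondary outcomes exploratory. No event rate is given, so the number of events affected among 70 children is unknown.

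**What to change.** 1. Change Visit 6 items 2d to 2f so that both arms are asked about events since randomisation (Visit 3).
2. In section 9.1, set the exposure for these counts to days from randomisation to Visit 6 or last contact, so that it matches the period asked about.
3. For participants already completed, recover the uncovered period from hospital and study records or a caregiver call, in the same way in both arms.
4. State when Visit 6 takes place for AHCL participants, who have no end-of-study blinded sensor to anchor it.

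The cost is one case report form wording change, a sentence each in sections 4.2 and 9.1, and a short look-back. No clinical management changes.
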